8.3.2 Non-Reportable Events

The hemodialysis population is characterized by frequent laboratory testing and a high rate of peridialytic hypotensive events requiring change in the dialysis prescription, adjustment of dry weight or change in dialysis-related medications. Due to the unique nature of this population, the following events are considered routine aspects of chronic dialysis therapy and they will not be considered to meet the criteria of SAE in this study except as noted:

- Anemia—will be reported only when hemoglobin <8.0 mg/dL
- Hyperphosphatemia—will be reported only when phosphate >9.5 mg/dL
- Hypocalcemia—will be reported only when serum calcium <7.0 mg/dL
- Hypercalcemia—will be reported only when serum calcium >11.0 mg/dL
- Hyperparathyroidism—will be reported only when PTH>1000 pg/mL
- Hypotension—will be reported only when requiring emergency room visit or hospitalization

- Hyperkalemia—will be reported only when >7.0 mEq/L
- Hypokalemia—will be reported only when <3.0 mEq/L

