4.2 Exclusion Criteria

- a) Serum potassium ≥ 6.5 mEq/L within 2 months prior to screening
- b) Unscheduled dialysis for hyperkalemia within the 3 months prior to screening
- c) Pre-dialysis hypotension defined as pre-dialysis SBP <100 mm Hg (seated measurement) within 4 weeks prior to the screening visit
- d) Recurrent intra-dialytic hypotension defined as either of the following:
 - o systolic blood pressure <80 mm Hg during ≥ 3 dialysis sessions in the 30 days prior to the screening visit, or
 - o treatment for hypotension or symptoms of hypotension during ≥ 3 dialysis sessions in the 30 days prior to the screening visit. For this criterion, hypotension is defined as systolic blood pressure <100 mm Hg.
- e) Mitral valve repair or replacement
- f) Severe mitral valve disease by echocardiography, coronary angiography or cardiac magnetic resonance imaging
- g) Anticipated kidney transplant, change to peritoneal dialysis, or transfer to another dialysis unit within 6 months
- h) Expected survival <6 months
- i) Allergy to study medications (ISD, HY, adenosine or dipyridamole)
- j) Active use of sildenafil, vardenafil or tadalafil
- k) Current severe aortic stenosis or other cause of LV outflow obstruction
- l) Pregnancy, anticipated pregnancy, or breastfeeding, confirmed by serum pregnancy test on the day of PET scan
- m) Incarceration
- n) Participation in another intervention study
- o) Use of monoamine oxidase inhibitors
- p) Contraindication to adenosine including

- 2nd or 3rd degree heart block, sick sinus syndrome or symptomatic bradycardia (without a functioning pacemaker)
- moderate or severe asthma
- chronic obstructive pulmonary disease

q) Active use of any of the study medications unless participant and physician willing to discontinue prior to enrollment.

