8.1.2 Serious Adverse Event

A *serious adverse event (SAE)* is any AE that is:

- fatal or results in death
- life-threatening
- requires or prolongs hospital stay
- results in persistent or significant disability or incapacity
- results in congenital anomalies or birth defects
- an important medical event*

*Important medical events are those that may not be immediately life threatening, but are clearly of major clinical significance.

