8.5 Medical Monitoring

The Clinical Center Principal Investigator will be responsible for overseeing the safety of the study at his/her site. This safety monitoring will include careful assessment and appropriate reporting of adverse events as noted above, as well as the construction and implementation of a site data and safety-monitoring plan. Medical monitoring will include a regular assessment of the number and type of serious adverse events.

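### Sections 8.1.2 and 8.3.2 conflict: a hospital admission for a listed laboratory event short of its cut-off is an SAE under one and not under the other

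*Combined protocol and SAP*

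**What the plan says.** Section 8.1.2 defines seriousness by outcome: "A *serious adverse event (SAE)* is any AE that is" fatal, life-threatening, disabling and so on, including one that "requires or prolongs hospital stay". It sets no laboratory threshold and does not refer to 8.3.2.

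Section 8.3.2 lists events regarded as routine in chronic dialysis and says that "they will not be considered to meet the criteria of SAE in this study except as noted". The list has eight lines. Seven are laboratory findings: anemia, hyperphosphatemia, hypocalcemia, hypercalcemia, hyperparathyroidism, hyperkalemia and hypokalemia. Each has a numeric exception and nothing else, for example "Hyperkalemia—will be reported only when >7.0 mEq/L" and "Hypokalemia—will be reported only when <3.0 mEq/L". The eighth is written by clinical consequence: "Hypotension—will be reported only when requiring emergency room visit or hospitalization".

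Under Section 8.4, SAE status triggers a report to the data coordinating center (DCC) within 24 hours. The DCC then arranges medical review and reports to the NIDDK and the DSMB. Section 8.5 adds: "Medical monitoring will include a regular assessment of the number and type of serious adverse events".

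**The concern.** The two sections answer the same question differently, and a site has no rule for choosing between them. Section 8.3.2 is the more specific text, so a coordinator would probably follow it. Because the hypotension line mentions hospitalization and the laboratory lines do not, the natural inference is that only the number counts for laboratory events.

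What is at stake is the SAE label and the speed of independent notice. Safety is a primary objective (Section 2.1), and the combination has not been studied in ESRD (Section 1.1). No interim analysis is planned (Section 7.4.3) and there is no external monitoring (Section 10.1), so the 24-hour SAE route is the main fast channel to anyone outside the site. The plan also treats potassium as a safety variable elsewhere. It is an entry criterion ("Serum potassium ≥ 6.5 mEq/L within 2 months prior to screening" is an exclusion), inability to follow it monthly can be a ground for withdrawal (Section 4.4.1), and its change is modeled with the safety outcomes (Section 7.4.1).

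**Working it through.** No sample size, power or event-rate figure is involved, so the check is textual. The test case is an admission for hyperkalemia at 6.8 mEq/L.

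1. Under 8.1.2, the event required a hospital stay, so it is an SAE. The laboratory value plays no part.
2. Under 8.3.2, hyperkalemia is listed, so it is not an SAE unless the noted exception applies. The exception is a value above 7.0; 6.8 is not above 7.0; no other exception is noted. The event is not an SAE.
3. The answers are opposite. The same follows for any hyperkalemia admission at or below 7.0 mEq/L.

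The other lines, with cut-offs and units as printed:

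| Line in 8.3.2 | Exception noted | Hospitalization exception | Admission that falls in the gap |
|---|---|---|---|
| Anemia | hemoglobin <8.0 mg/dL | none | at 8.0 or above |
| Hyperphosphatemia | >9.5 mg/dL | none | at 9.5 or below |
| Hypocalcemia | <7.0 mg/dL | none | at 7.0 or above |
| Hypercalcemia | >11.0 mg/dL | none | at 11.0 or below |
| Hyperparathyroidism | PTH >1000 pg/mL | none | at 1000 or below |
| Hyperkalemia | >7.0 mEq/L | none | at 7.0 or below |
| Hypokalemia | <3.0 mEq/L | none | at 3.0 or above |
| Hypotension | by consequence | emergency room or hospital | none for admissions |

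Next, is there text that restores the 8.1.2 criterion? Section 8.3.1 says that calling an event anticipated does not stop it from being an SAE, but that note concerns its own list and the definition of Unanticipated Problems. It does not qualify 8.3.2. No section says that 8.1.2 prevails.

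Last, what happens to an admission that loses SAE status?

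- Adverse event log: kept. Section 8.3 puts adverse events on the log form, and 8.1.1 counts abnormal laboratory findings as adverse events.
- Study contacts: kept. Section 6.4 names hospitalizations among the events sought at Weeks 1, 2, 4 and 16, and adverse events are reviewed at the later contacts.
- Treatment-emergent composite (Section 2.1): kept, since it counts hospitalizations without restriction by cause.
- 24-hour report to the DCC and the SAE reports to the NIDDK and DSMB (Section 8.4): missed.
- SAE count in site medical monitoring (Section 8.5): missed.

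**The case against.** The strongest reply is that 8.3.2 concerns routine findings from frequent laboratory testing. An emergency admission is not routine, so it falls outside the list and 8.1.2 governs. That reading is possible. It is weakened by the hypotension line, which would not need its hospitalization wording if admissions were outside the list anyway. It is also possible that 8.3.2 is a deliberate study-specific carve-out. Even then, its exceptions are incomplete and the order of precedence is unstated.

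A second reply is that oversight does not rest on SAEs alone. This stands. Section 8.5.1 has the DSMB review safety data generally, Section 9.1.2 provides for adverse event and DSMB reports, and Section 8.5 includes assessment of adverse events as well as the SAE count. A reader might infer that these admissions vanish from the safety data; the documents do not support that.

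A third reply is that Section 1.4 expects no particular metabolic or hematologic harm from the drugs, while hypotension, the expected harm, has the exception. This also stands and lowers the likely number of affected events.

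Three further inferences should be resisted:

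- With 8 per arm, one might say each dropped admission lowers that arm's SAE incidence by 1/8 = 12.5 percentage points. That holds only if the participant has no other SAE, and SAE incidence is not among the safety endpoints in Section 3.2.1.
- One might place the potassium gap at 6.5 to 7.0 mEq/L. The 6.5 figure is an eligibility limit, not a seriousness threshold; the literal gap is any admission at or below 7.0.
- One might say that an asymptomatic PTH just above 1000 becomes an SAE. Section 8.3.2 mixes the language of reporting with that of SAE criteria, and the wording is too ambiguous to support this.

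**Conclusion.** The conflict is real and affects seven of the eight lines in 8.3.2. Read literally, an admission for a listed laboratory event short of its cut-off is not an SAE, although 8.1.2 says it is. The loss is limited to the SAE classification, the 24-hour DCC report, the SAE reports to the NIDDK and DSMB, and the SAE count in Section 8.5. The admission itself stays in the safety data. The number of events cannot be sized, because the documents give no rate of such admissions. The conclusion assumes that sites apply 8.3.2 as written. It also assumes that no accompanying event, such as an arrhythmia, is reported as an SAE in its own right; Section 8.3 makes that less likely by recording findings of one event under one diagnosis name. The point is worth correcting because safety is a primary objective and the correction is small.

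**What to change.** Reconcile the two sections by adding one sentence to the lead-in of 8.3.2: any listed laboratory event that meets a criterion in 8.1.2 (for example hospitalization or a threat to life) is reported as an SAE whatever the laboratory value. Leave adverse event recording under 8.1.1 unchanged. In particular, the 8.3.2 cut-offs should not be turned into thresholds for recording adverse events, because 8.1.1 has none and that would narrow what is captured. The change concerns reporting only and touches no dose, treatment rule or laboratory cut-off. The cost is one sentence in an amendment and possibly some additional SAE reports, whose number the documents do not allow to be estimated.

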8.4 Reporting of Serious Adverse Events and Unanticipated Problems

Study sites are required to report SAEs to the DCC within 24 hours of first knowledge of the event. To report such events, an SAE form will be completed by the investigator and faxed or emailed to the DCC. The DCC will facilitate the timely medical review and reporting of the event, and provide reports to the NIDDK and the Data and Safety Monitoring Board (DSMB) in accordance with DSMB-approved study policies and regulatory requirements (see **Section 8.5.1** for details of the DSMB).

The investigator will keep a copy of the SAE form on file at the study site. At the time of the initial report, the following information should be provided:

▪ Study identifier▪ Study Center▪ Participant number▪ A description of the event▪ Date of onset▪ Current status	
▪ Whether study treatment was discontinued▪ The reason why the event is classified as serious▪ Investigator assessment of the association between the event and study participation
--	---

Within the following 7 days, the investigator will provide further information on the SAE or the unanticipated problem in the form of a written narrative. This should include a copy of the completed SAE form, and any other diagnostic information that will assist in the understanding of the event. Significant new information on ongoing serious adverse events should be provided promptly to the DCC.

If a participant becomes pregnant while participating in the study it will be reported as an adverse event and will trigger the collection of additional documentation about the pregnancy. Pregnancy outcomes will be collected, including the outcome of the infant and if the pregnancy was terminated. This information will be submitted to the University of Pennsylvania IRB, and to the local site IRB as required.

SAEs that are still ongoing at the end of the study period must be followed up to determine the final outcome. Any SAE that occurs after the study period and is considered to be possibly related to the study treatment or study participation should be recorded and reported immediately.

8.4.1 Investigator Reporting to the IRB

The site investigator will report SAEs and Unanticipated problems to the clinical center IRB in accordance with the reporting requirements of the local IRB or with the Office of Human Research Protections (OHRP) guidelines, whichever is sooner. OHRP recommends that:

- 1) Unanticipated problems that are serious adverse events should be reported to the IRB within 1 week of the investigator becoming aware of the event; and

- 2) Any other unanticipated problem should be reported to the IRB within 2 weeks of the investigator becoming aware of the problem.

Reporting Process

Unanticipated problems posing risks to participants or others as noted above will be reported using the appropriate IRB-designated form or as a written report of the event (including a description of the event with information regarding its fulfillment of the above criteria, follow-up/resolution and need for revision to consent form and/or other study documentation).

Copies of each report and documentation of IRB notification and receipt will be maintained in the Clinical Center Investigator's study file.

Other Reportable Events:

- Any adverse event that would cause the study's Steering Committee to modify the protocol or informed consent form, or would prompt other action by the IRB to assure protection of human participants.
- Information that indicates a change to the risks or potential benefits of the research, in terms of severity or frequency.
- Breach of confidentiality
- Change to the protocol made without prior IRB review to eliminate apparent immediate hazard to a research participant.
- Incarceration of a participant when the research was not previously approved under 45 CFR part 46 subpart C and the investigator believes it is in the best interest of the participant to remain in the study.
- Complaint of a participant when the complaint indicates unexpected risks or the complaint cannot be resolved by the research team.
- Protocol violation (meaning an accidental or unintentional deviation from the IRB approved protocol) that in the opinion of the investigator placed one or more participants at increased risk, or affects the rights or welfare of participants.

8.4.2 DCC Notification to Study Investigator

The DCC will notify the study principal investigator, in a written safety report, of any adverse event that meets the criteria of an unanticipated and related event as described in **Section 8.1.3**.

8.5 Medical Monitoring

The Clinical Center Principal Investigator will be responsible for overseeing the safety of the study at his/her site. This safety monitoring will include careful assessment and appropriate reporting of adverse events as noted above, as well as the construction and implementation of a site data and safety-monitoring plan. Medical monitoring will include a regular assessment of the number and type of serious adverse events.

8.5.1 Independent Data and Safety Monitoring Board (DSMB)

The information provided in this section of the protocol is a general description of the DSMB responsibilities and processes. A DSMB charter for the Hemodialysis Novel Therapies Consortium includes additional detail.

A DSMB has been established by the NIDDK and provides input to the Institute. The DSMB is comprised of individuals with expertise in clinical trials design and methodology, biostatistics, clinical nephrology and other relevant medical specialties. The DSMB members are not affiliated with the study and are appointed by the NIDDK. DSMB members will be free of conflicts of interest that could be affected by the outcomes of the study. During the study, DSMB members who develop real or perceived conflicts of interest that impact objectivity will disclose them to NIDDK project officers, who will arrange for replacement of the member, if indicated.

The DSMB will review the protocol before initiation of the study. After initial approval during the course of the study, the primary responsibilities of the DSMB will be to:

- 1) Review safety data and provide input to protect the safety of the study participants;
- 2) Provide input on major changes to the research protocol and plans for data and safety monitoring;
- 3) Provide input on the progress of the study, including periodic assessments of data quality and timeliness, participant recruitment, accrual and retention, participant risk versus benefit, performance of the study site, and other factors that may affect study outcomes;
- 4) Consider factors external to the study when relevant information becomes available, such as scientific or therapeutic developments that may have an impact on the need for continuation of the study, safety of the participants or the ethics of the study;
- 5) Provide input on modification of the study protocol or possible early termination of the study because of attainment of study objectives, safety concerns, or inadequate performance (such as enrollment and retention problems).

9 Data Management

An internet based data management system will be used to collect, store and manage study data. Site personnel will enter data directly into the database using electronic case report forms (CRFs) developed by the PI, statistician, and study investigator. Data entry screens will incorporate range and logical edit checks, within and across forms. Data entry will be followed with manual and programmed checks and edits for errors and omissions. A data monitoring plan will serve as a reference guide for the development of case report forms (paper and electronic versions), data management conventions, reporting, data dictionaries, supporting meta data, as well as project closeout activities, communication and coordination plans among the study teams and staff.

9.1.1 Quality Control Activities

Manual of Procedures (MOP) - The MOP will describe the sequence of study conduct and provide detailed instruction for the performance of screening, baseline, enrollment, treatment allocation and follow-up procedures. The MOP will provide instruction in case report form completion, use of the

electronic data management system, and collection, documentation and transfer of specimens and tests to laboratories and reading centers.

Internal quality control procedures - A data validation plan, rule set specifications, and programming logic to implement data validation rules will be implemented.

9.1.2 Routine reports

The study team will develop a set of standard enrollment, tracking, quality review, and safety monitoring reports. Adverse event reports, DSMB reports and reports for statistical analysis will be developed and produced on an appropriate schedule.

9.2 Data Security

The data management system will be designed to prevent unauthorized access to trial data and to prevent data loss due to equipment failure or catastrophic events. The procedures to do so encompass user account management, user privilege assignment, data loss prevention (database backup), and DMS change management. User access will be controlled by assignment of confidential usernames, passwords.

Study data collected at the clinical sites will be entered into a web-based electronic data capture system. This data management system uses a secure connection between the client browser at the clinical site and the web server at the DCC. Data transmitted over this connection is authenticated by the use of digital certificates and is encrypted as it travels the Internet.

The statistical project team will collaborate with the Investigational Drug Service (IDS) to protect the blinding of treatment assignments and electronic access to information that could indirectly or directly lead to unblinding treatment assignment or codes. Internal access to such information is stored in password-protected files.

9.2.1 Confidentiality

Information about study participants will be kept confidential and managed according to the requirements of the Health Insurance Portability and Accountability Act of 1996 (HIPAA). Those regulations require a signed participant authorization informing the participant of the following:

- a. What protected health information (PHI) will be collected from participants in this study
- b. Who will have access to that information and why
- c. Who will use or disclose that information
- d. The rights of a research participant to revoke their authorization for use of their PHI.

In the event that a participant revokes authorization to collect or use PHI, the investigator, by regulation, retains the ability to use all information collected prior to the revocation of participant authorization. For participants who have revoked authorization to collect or use PHI, attempts should be made to obtain permission to collect at least vital status (i.e. that the participant is alive) at the end of their scheduled study period.

9.3 *Source Documents*

Source data is all information, original records of clinical findings, observations, or other activities in a clinical trial necessary for the reconstruction and evaluation of the trial. Source data are contained in source documents. Examples of these original documents, and data records include: hospital records, clinical and office charts, laboratory notes, memoranda, participants' diaries or evaluation checklists, pharmacy dispensing records, recorded data from automated instruments, copies or transcriptions certified after verification as being accurate and complete, microfiches, photographic negatives, microfilm or magnetic media, x-rays, participant files, and records kept at the pharmacy, at the laboratories, and at medico-technical departments involved in the clinical trial.

9.3.1 *Maintaining Anonymity of Submitted Medical Records*

Clinical site personnel will de-identify all medical records before sending them to the data coordinating center.

9.3.2 *Data Sharing*

It is required that research results generated under sponsorship by NIH are made available to the scientific community and public in a timely manner. The primary method by which data are shared with the scientific community is through peer-reviewed publications and presentation at meetings. In addition, data and results created from NIH supported research will be submitted to NIH in the annual progress reports required under the terms and conditions of this award. This study will also be registered with clinicaltrials.gov.

Data from this study will be submitted to the NIDDK Data Repository in accordance with the NIDDK Data Sharing policy. The policy requires that data sets be transferred no later than 2 years after study completion or 1 year after publication of the primary results, whichever comes first. Through the repository, the study data will be made available to external investigator.

9.3.3 *Records Retention*

The site investigator will retain study documents, including participant files and Investigational Binders, for at least 5 years after the close of the study, or longer depending on site institutional requirements.

10 *Study Monitoring, Auditing, and Inspecting*

10.1 *Study Monitoring Plan*

Given the small size and single center nature of the study, there will be no external monitoring. However, the principal investigator will allocate adequate time for monitoring activities, study binders, and case report forms with study personnel.

10.2 *Auditing and Inspecting*

The investigator will permit study-related monitoring, audits, and inspections by the EC/IRB, the NIH, government regulatory bodies, and University compliance and quality assurance groups of all study related documents (e.g. source documents, regulatory documents, data collection instruments, study

data etc.). The investigator will ensure the capability for inspections of applicable study-related facilities (e.g. pharmacy, diagnostic laboratory, etc.).

Participation as an investigator in this study implies acceptance of potential inspection by government regulatory authorities and applicable University compliance and quality assurance offices.

11 Ethical Considerations

This study is to be conducted according to US and international standards of Good Clinical Practice (FDA Title 21 part 312 and International Conference on Harmonization guidelines), applicable government regulations and Institutional research policies and procedures.

This protocol and any amendments will be submitted to a properly constituted independent Ethics Committee (EC) or Institutional Review Board (IRB), in agreement with local legal prescriptions, for formal approval of the study conduct. The decision of the EC/IRB concerning the conduct of the study will be made in writing to the investigator and a copy of this decision will be provided to the sponsor before commencement of this study.

All participants for this study will be provided a consent form describing this study and providing sufficient information for participants to make an informed decision about their participation in this study. This consent form will be submitted with the protocol for review and approval by the EC/IRB for the study. The formal consent of a participant, using the EC/IRB-approved consent form, must be obtained before that participant undergoes any study procedure. The consent form must be signed by the participant or legally acceptable surrogate, and the investigator-designated research professional obtaining the consent.

12 Study Finances

12.1 *Funding Source*

This study is financed through a grant from the National Institute of Diabetes and Digestive and Kidney Diseases of the U.S. National Institutes of Health.

12.2 *Conflict of Interest*

The study investigator will follow the conflict of interest policies of the National Institutes of Health as well as their home institution. Any investigator who has a potential conflict of interest with this study (patent ownership, royalties, or financial gain greater than the minimum allowable by their institution, etc.) must have the conflict reviewed by a properly constituted Conflict of Interest Committee with a Committee-sanctioned conflict management plan that has been reviewed and approved by the study sponsor prior to participation in this study.

12.3 *Participant Stipend*

Participants will be compensated \$400 plus travel expenses for time and effort required to participate in the study. Stipends will be distributed in equal payments after the completion of the first and second PET scans.

13 Publication Plan

Study results will be published in peer reviewed manuscript and presented in preliminary form at annual meetings of national societies or research meetings. Every effort will be made to publish results within a year of final receipt of locked study data sets.

14 References

